**Comparison of Electrophysiologic And Ultrasound Guidance For Onabotulinum Toxin A
Injections in Focal Upper Extremity Dystonia And Spasticity**

PI: [name]

NCT02334683

Document Date: 9-2-2014

Protocol

Comparison of Electrophysiologic Guidance and Ultrasound Guidance for Botulinum Toxin Injections

Brief Summary of Research (250-400 words):

This is a study to investigate the use of two targeting techniques for botulinum toxin (BoNT) injection for the treatment of focal hand dystonia and upper limb spasticity: Electrophysiologic guidance, using electrical stimulation, and ultrasound. Subjects will be selected from the clinical programs of both Icahn School of Medicine at Mount Sinai and the National Institutes of Health who are already receiving onabotulinum toxin A injections clinically. The study will consist of four visits. Visit one consists of screening subjects who will then be consented and randomized to one of the two treatment techniques for their onabotulinum toxin A injection: 1) Electrophysiologic guidance using electrical stimulation or 2) ultrasound. Visit 2 will occur at week 4 where the subjects will return for a follow up visit to have blinded evaluator measurements of efficacy and strength and capture safety data. Visit 3 will be at week 12 when subjects will cross over and have the alternate treatment technique during their onabotulinum toxin A injection. Visit 4 will occur at week 16 as the final assessment where subjects will have measurements of efficacy and strength and capture safety data by the blinded evaluator.

1) Objectives:

Research Question:

Hypothesis: Neither Ultrasound or electrical stimulation will not show significant differences in the outcome measures.

1) Improvement in dystonia or spasticity severity on visual analogue scale.

Secondary objectives

1. Duration of the injection procedure
2. Weakness in targeted and adjacent muscles after the procedure
3. Number of needle sticks and needle re-direction within a muscle required for delivery with each technique
4. Side effects with each technique
5. Patient self-reported satisfaction with each procedure
6. Physician global impression of change
7. For dystonia, physician rated "Arm Dystonia Disability Scale"
8. For spasticity, physician rated Modified Ashworth scale
9. Patient discomfort assessed on a visual analog scale.

2) Background

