At the NIH site, patients will be introduced to the research project from the BoNT clinic, including the neurology and movement disorders practitioners at Suburban Hospital, Holy Cross Hospital, George Washington University Medical Center, Georgetown University Hospital, Johns Hopkins University Medical Center, The Parkinson Disease and Movement Disorders Center of Maryland, University of Maryland and others.

Subjects potentially interested will be provided information about the study, copy of the consent form will be provided which subjects can review and bring home for family or friends to review. They will have the opportunity to contact the investigators at the Icahn School of Medicine or the NIH for questions. We anticipate recruiting a total of 30 subjects with 15 subjects at each site within one year.

b) Inclusion and Exclusion Criteria

Inclusion criteria

- Confirmed diagnosis of focal upper extremity dystonia (FHD) or upper limb spasticity
- Stable onabotulinumtoxinA dose regimen with a stable response as judged by the physician and patient for at least 2 treatment sessions.
- Age 18 and above

Exclusion criteria

- Contraindications to botulinum toxin
- Pregnancy or nursing
- Cognitive impairment that prevents reliable outcome measures of self-report

[figure not shown]
c) Number of Subjects

The study will enroll a total of 30 patients, with 15 patients at each site. Target number of patients to be treated and complete the study will be 18 subjects (to have sufficient statistical power).

d) Study Timelines

This is a randomized cross-over study, with two study sites. 4 outpatient visits of approximately 30-60 minutes each will take place over 16- 24 weeks. All NIH patients will also be enrolled in protocol 85-N-0195, and botulinum injections will be done under that protocol.

An outline of the procedures is depicted in the figure below:

The study anticipates enrollment of the first subject in February 2015. The study team anticipates an enrollment period of approximately 36 months with the last patient to be enrolled Dec. 2020 with the primary analysis completed by June 2021.

Study Endpoints

Outcome measures

Primary outcome measures

Improvement in dystonia or spasticity severity on a physician and patient self-reported visual analog scale.

Secondary outcome measures

- (1) Duration of the injection procedure as follows:
 - (a) E-Stim: time from needle In to needle Out

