Repeated measures ANOVA will be used for the primary outcome. Patients who do not complete all 4 visits will be replaced, and all subjects will be included in the safety analysis. We will use $p < 0.05$ as significance threshold. No interim analysis is planned.

Power analysis

Calculations are based on a α of 5% and a β of 80%, and the published SD for ona-BoNT-A therapy of 20%. There is an expected variation of 15% for the procedure. We hypothesize that US will demonstrate non-inferiority in comparison to E-stim based on previous experience performing the procedures. A total of 18 subjects (9 from each site) are needed to show the desired 15% variation. 15 subjects will be enrolled at each site to allow for screen failures and dropouts.

h) Provisions to Monitor the Data to Ensure the Safety of subjects

Adverse events will be reviewed at every visit. Patients will be asked specifically about pain or weakness. Patients will also have the option to contact the investigators between scheduled visits to report unanticipated events.

The procedures will be stopped if an individual reports any unexpected adverse event NCI grade 3 or higher.

Serious or unexpected adverse events and other unanticipated problems will be reported orally as soon as possible and in writing within 7 days if life-threatening and within 15 days otherwise. Expected or non-serious adverse events will be reported at the time of continuing review. Adverse events will be reviewed at every visit. Patients will be asked specifically about pain or weakness. Patients will also have the option to contact the investigators between scheduled visits to report unanticipated events.

The procedures will be stopped if an individual reports any unexpected adverse event NCI grade 3 or higher.

Serious or unexpected adverse events and other unanticipated problems will be reported orally as soon as possible and in writing within 7 days if life-threatening and within 15 days otherwise. Expected or non-serious adverse events will be reported at the time of continuing review.

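### The stated aim is non-inferiority of ultrasound, but the only decision criterion is an ANOVA at p < 0.05, with no named margin or confidence-limit rule

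*Combined protocol and SAP*

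**What the plan says.** All statements are in the combined protocol and SAP.

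- **Section 1, Objectives.** The hypothesis reads "Neither Ultrasound or electrical stimulation will not show significant differences in the outcome measures". Despite the double negative, it predicts no significant difference.
- **Study Endpoints.** The primary outcome is "Improvement in dystonia or spasticity severity on a physician and patient self-reported visual analog scale".
- **Section 5g, Analysis of data/study outcomes.** "Repeated measures ANOVA will be used for the primary outcome", and "We will use $p < 0.05$ as significance threshold". No other criterion for the primary outcome is given.
- **Section 5g, Power analysis, inputs.** Alpha is 5%, with "a β of 80%, and the published SD for ona-BoNT-A therapy of 20" percent.
- **Section 5g, Power analysis, the 15% figure.** It is introduced without being called a margin: "There is an expected variation of 15% for the procedure".
- **Section 5g, Power analysis, aim.** The aim is stated next, again with no margin attached: "We hypothesize that US will demonstrate non-inferiority in comparison to E-stim based on previous experience performing the procedures".
- **Section 5g, Power analysis, sample size.** The number of patients is then tied back to the same percentage: "A total of 18 subjects (9 from each site) are needed to show the desired 15% variation".
- **Sections 5c and 5g, numbers.** Thirty patients are enrolled, 15 per site, with 18 as the target to complete. Patients who miss any of the four visits are replaced.

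**The concern.** The aim and the decision criterion do not match. Non-inferiority is shown when the data exclude a US deficit as large as a margin fixed in advance. An ANOVA at p < 0.05 asks whether the two techniques differ. Failing to find a difference may mean that they are alike, or only that the estimate is imprecise.

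Section 1 expects no significant difference and section 5g expects non-inferiority. A non-significant p-value could therefore be taken to confirm both, and nothing in the text prevents that. The comparison of techniques is the purpose of the trial, so this rule decides what the trial may conclude.

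The printed β is a separate and smaller matter. Read literally, 80% is the chance of missing the effect, which would mean 20% power.

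**Working it through.** **Inputs.** From the power analysis: alpha 5%, SD 20%, the 15% figure, and N = 18. Assumptions, because the text does not settle them: 15 is the non-inferiority margin in VAS points; 20 is the SD of the within-patient US minus E-stim difference (SDdiff); intervals are two-sided 95%, equivalent to a one-sided 2.5% test. The design is a crossover, so the comparison is paired.

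**Step 1: reproduce 18.**

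- Normal formula: n = (1.96 + 0.8416)² × 20² / 15² = 7.849 × 400/225 = 13.95, so 14.
- Noncentral t, 80% power: 16 patients (80.1%) with n − 1 degrees of freedom, or 17 (82.4%) with n − 2 for the crossover.
- At n = 18, power is 85.0%.

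The stated 18 is therefore consistent with 80% power. Literal 20% power would need only about 5 patients, so 18 did not come from a β of 80%.

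**Step 2: where the two readings disagree at 18 completers.** The half-width of the 95% interval is t(0.975, 17) × SDdiff/√n = 2.110 × 20/√18 = 9.95.

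- A US deficit is non-significant if it is smaller than 9.95.
- A 15-point deficit is excluded only if the observed deficit is below 15 − 9.95 = 5.05.

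Observed deficits of about 5.1 to 9.9 points are thus non-significant but do not exclude the margin. For example, an observed deficit of 8 gives −8 ± 9.95, or −17.9 to +1.9 after rounding.

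**Step 3: chance that a true 15-point deficit is non-significant.** This is the noncentral t probability with noncentrality 15/(SDdiff/√n). At n = 18 and SDdiff 20 the noncentrality is 15/4.714 = 3.18.

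| Completers | SDdiff | Non-significant | Limit rule met |
|---|---|---|---|
| 18 | 16 | 3.7% | 2.5% |
| 18 | 20 | 15.0% | 2.5% |
| 18 | 24 | 29.5% | 2.5% |
| 18 | 28.3 | 43.6% | 2.5% |
| 24 | 20 | 6.0% | 2.5% |
| 30 | 20 | 2.2% | 2.5% |

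The last column is 2.5% by construction, because the true deficit equals the margin. An SDdiff of 28.3 is 20 × √2, the value if 20 were a per-treatment SD with no within-patient correlation. That is a pessimistic case: response is stable, muscles and dose are unchanged, and each subject keeps one rater.

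**Step 4: more completers.** At n = 30 and an observed SD of 20, the half-width is 7.47. Any non-significant deficit is below 7.47, so its lower limit lies above −(7.47 + 7.47) = −14.94. The two readings then agree. At n = 24 the band of disagreement is narrow, about 6.6 to 8.4 points.

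**The case against.** The strongest reply has four parts.

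*The planned model is adequate.* A repeated measures ANOVA yields the within-patient difference and its interval. This stands. A reader might infer that the stated test cannot support the aim, but the same model gives the limit that is needed. What is missing is the statement of how its output will be read.

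*The 15% is plainly the margin.* The non-inferiority sentence sits between the two sentences that give 15%, so this is the natural reading. The word is never used, however, and the wording could equally describe a difference to detect. Even if 15% is the margin, nothing ties the ANOVA result to it.

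*The harm is shown at the minimum number of completers.* This largely stands. Thirty are enrolled and non-completers are replaced, so 18 is a floor. At SDdiff 20 the problem nearly disappears by 30 completers. But the plan names 18 as its target, and the risk is larger if SDdiff exceeds 20. The documents do not establish the larger values used above.

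*No sentence says that non-significance will be treated as proof.* Correct. Section 1 states a prediction. The concern is that the plan leaves that reading open, not that it commits to it.

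Two further inferences are tempting. One is that the trial has 20% power; the reproduction of 18 shows that it was sized for about 80%. The other is that 18 is too few; it suffices if 20% is the SD of the within-patient difference, and the documents do not show otherwise.

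One stretch of text, next to the safety-monitoring provisions, was not available. A margin or rule there is unlikely but cannot be excluded.

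**Conclusion.** The concern holds as a gap in the decision rule, and the plan should be amended. It states a non-inferiority aim, gives only a significance threshold for the primary outcome, and names neither a margin nor a confidence-limit rule in the text supplied.

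The size is conditional on a margin of 15 and on SDdiff. At SDdiff 20 and the targeted 18 completers, reading non-significance as success would pass a true 15-point US deficit six times as often as a limit rule (15.0/2.5 = 6). By 30 completers there is no excess.

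The printed β is wrong, but as a label only. Design, model and sample size can stand.

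**What to change.** Keep the repeated measures (crossover) model and add to section 5g:

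> Non-inferiority of US will be concluded only if the lower limit of the two-sided [95%; 90% if a one-sided 5% level was used] confidence interval for the within-patient US minus E-stim difference in VAS improvement, from the planned model, lies above minus the margin [15%, if the sponsor confirms that this is what 15% denotes]. A non-significant ANOVA is not evidence of non-inferiority.

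Reword the section 1 hypothesis to match. In the power analysis, replace the β of 80% with power 80% (β 20%).

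This is a text change plus the sponsor's confirmation of what 15% denotes and which level was used. No patients beyond the planned 30 are needed. The real cost is that success becomes harder to claim. With 18 completers, SDdiff 20 and no true difference, the ANOVA is non-significant 95% of the time, while the limit rule is met 85% of the time.

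### The plan hypothesises non-inferiority of ultrasound, but its only primary rule is a difference test at p < 0.05, with no declared margin and no confidence-limit rule

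*Combined protocol and SAP*

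**What the plan says.** Three places in the combined protocol and SAP bear on how the primary comparison will be concluded.

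- **Section 1, Objectives.** The hypothesis reads "Neither Ultrasound or electrical stimulation will not show significant differences in the outcome measures". The double negative aside, the evident sense is that no significant differences are expected.
- **Section 5g, Analysis of data/ study outcomes.** "Repeated measures ANOVA will be used for the primary outcome", with significance at p < 0.05. Model terms, sidedness and a confidence interval are not given.
- **Section 5g, Power analysis.** "We hypothesize that US will demonstrate non-inferiority in comparison to E-stim based on previous experience performing the procedures". The same paragraph gives α of 5%, a stated β of 80% (evidently power), and "the published SD for ona-BoNT-A therapy of 20"%. It adds "There is an expected variation of 15% for the procedure" and concludes "A total of 18 subjects (9 from each site) are needed to show the desired 15% variation".

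Section 5c repeats 18 as the completer target; 30 is the enrolment figure. The primary outcome (Study Endpoints) is "Improvement in dystonia or spasticity severity on a physician and patient self-reported visual analog scale".

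**The concern.** A non-inferiority claim needs two things fixed in advance: the largest deficit that would be tolerated, and a rule that the confidence limit on the unfavourable side must exclude it. The plan has neither. An ANOVA p-value addresses a different question, whether the difference is zero.

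The result that the sponsor expects, with the two techniques performing alike, will usually give p ≥ 0.05. The plan then has no valid basis for saying that ultrasound is non-inferior or that the techniques do not differ. If non-significance is read as similarity, noisier ratings or fewer completers make that conclusion easier to reach. A margin chosen after the data are seen could be fitted to the result.

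**Working it through.** **1. What each result supports under the rule as written.**

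| Result | Bearing on the hypotheses |
|---|---|
| p < 0.05, ultrasound better | The whole 95% CI favours ultrasound, so non-inferiority holds at any positive margin |
| p ≥ 0.05 | Puts no stated bound on a deficit; supports neither hypothesis |
| p < 0.05, ultrasound worse | Shows a deficit, but not whether it exceeds a tolerable amount |

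**2. The plan's own figure.** Inputs from the Power analysis: difference 15, SD 20, α 0.05, power 0.80. Assume a paired comparison, a two-sided test, and that 20 is the SD of the within-patient difference (SDd). The normal approximation is n = [(1.960 + 0.842) × 20 / 15]² = 13.95, so 14. The noncentral t gives 16 (df n − 1) or 17 (df n − 2, a crossover model with a period term). These are close to the stated 18, where power is 85%.

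**3. Can the sample size reveal whether 15% was meant as a margin?** With no true difference, a 15-point margin and one-sided 0.025, the calculation is the same: 17 completers, and 85% power at 18. At one-sided 0.05 it gives 13. The figure of 18 therefore does not settle the question.

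**4. How often a real deficit would be non-significant.** Assumptions:

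- 15% means 15 VAS points.
- There are 18 completers, with df = 16.
- The ANOVA test is two-sided at 0.05.
- SDd is varied, because the documents do not say which SD the 20% is and give no correlation. If 20 is a single-measurement SD with within-patient correlation r, then SDd = 20 × √(2(1 − r)). SDd = 20 also covers the case where 20% is already the SD of the difference.

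With SE = SDd/√18, the noncentrality is 15/SE, and the critical value is t(0.975, 16) = 2.120. The non-significance column assumes that ultrasound is truly 15 points worse; the power columns assume no true difference.

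| r | SDd | SE | 15/SE | 95% CI half-width | P(p ≥ 0.05), true deficit 15 | NI power, margin 15, one-sided 0.025 | Same, one-sided 0.05 |
|---|---|---|---|---|---|---|---|
| 0.7 | 15.5 | 3.65 | 4.11 | 7.7 | 3% | 97% | 99% |
| 0.5 | 20 | 4.71 | 3.18 | 10.0 | 15% | 85% | 92% |
| 0.3 | 23.7 | 5.58 | 2.69 | 11.8 | 29% | 71% | 82% |
| 0 | 28.3 | 6.67 | 2.25 | 14.1 | 44% | 56% | 69% |

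With a true deficit exactly at the 15-point margin, a 95% CI rule falsely concludes non-inferiority in 2.5% of trials at every SD.

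**5. A smaller margin.** For 80% power with a 10-point margin, the completers needed are 21, 34, 46 or 65 at one-sided 0.025, and 17, 27, 37 or 51 at one-sided 0.05, in the same SD order. At one-sided 0.025 every figure exceeds the 18-completer target. At one-sided 0.05 only the lowest SD falls within it.

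**The case against.** **The 15% may be the margin.** The non-inferiority sentence stands between the two sentences on 15%, so this could be a mislabelled margin rather than an absent one. That stands as a possibility, and the sponsor can confirm it. It does not remove the gap. The text treats 15% as something expected and to be shown, whereas a margin is something to be excluded, and no conclusion is tied to it.

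**The ANOVA can supply what is needed.** Correct. A repeated measures model on crossover data yields the within-patient difference and its confidence interval. The model is not at fault; the missing parts are the margin and the rule.

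**The harm may be small.** Also fair. Patients must have a stable response at entry (section 5b), and each keeps the same blinded rater (section 5e, Visit 2), so high within-patient correlation is plausible. At the lowest SD the non-significance rate is 3%. The plan also replaces patients who do not complete all four visits, which limits a shortfall in completers.

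Stronger readings are tempting but not supported:

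- *No result could support non-inferiority.* A significant result favouring ultrasound would. The Background says that earlier studies suggested ultrasound can improve outcomes. With a true 10-point advantage, SDd 20 and 18 completers, such a result occurs in 51% of trials.
- *The plan will count p ≥ 0.05 as success.* It does not say so; the wording of the Objectives only invites that reading.
- *The trial is too small for non-inferiority.* That depends on a margin, an alpha and an SD that the documents do not fix. With a 15-point margin and SDd 20, 18 completers are adequate.

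**Conclusion.** The point stands and should be fixed before analysis. The stated rule supports the non-inferiority hypothesis only through superiority of ultrasound. A non-significant result supports neither that hypothesis nor the one in the Objectives, and a significant result against ultrasound leaves the size of the deficit unjudged. This follows from the logic of the test and does not depend on any SD.

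The practical size does depend on assumptions. The range of 3% to 44%, against 2.5% under a confidence-limit rule, rests on 15% meaning 15 VAS points, on 18 completers, on a two-sided 0.05 test, and on the assumed SDs. It describes misleading conclusions only if non-significance is taken as similarity. A section of the safety-monitoring text was not available for this check; it is an unlikely place for a margin.

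**What to change.** Make the Objectives and the Power analysis state the same primary hypothesis, by one of three routes.

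- **A. Non-inferiority.** Keep the crossover ANOVA. Report the within-patient ultrasound minus E-stim difference on the primary VAS with its confidence interval, and state the level (a two-sided 95% interval corresponds to one-sided 0.025). Conclude non-inferiority only if the limit unfavourable to ultrasound excludes the margin.
- **B. Two-sided equivalence.** Conclude it only if the whole interval, at a stated level, lies within plus and minus the margin.
- **C. Difference test only.** Delete the non-inferiority sentence and also reword the Objectives so that they do not claim to confirm the absence of a difference. Deleting the sentence alone would leave the Objectives with a claim the test cannot establish.

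For A or B, fix and justify the margin in VAS units before analysis, using 15% only if the sponsor confirms it as the margin, and restate power for that margin, alpha and SD. Under every route, state that p ≥ 0.05 is not evidence of similarity. Whether the physician or the patient VAS is primary is a separate matter.

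The cost is text in the Objectives, analysis and power paragraphs, plus a clinical justification of the margin for A or B. No new assessments are needed. The trial may prove inconclusive, as the power figures above show. Any restated power should be set against the target of 18 completers, not the 30 enrolled, since 30 already allows for screen failures and dropouts.

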- 3) Accumulated safety and data information will be reviewed by the monitors during the monthly study team calls.
- 4) The study does not require any stopping rules for interrupting the study or altering the study design. The treatments are standard of care.
- 5) Onabotulinumtoxin A is not under study. The subjects will receive their standard clinical treatment.
- 6) AEs will be classified as mild, moderate or severe based upon the following criteria: Mild = symptoms do not alter the subject’s normal functioning, Moderate= symptoms produced some degree of impairment to function but are not dangerous, uncomfortable or embarrassing to the subject, Severe = symptoms are dangerous to the subject’s well-being and causes significant impairment of function or incapacitation.

The relationship of the AE to the treatment will be classified as follows:
Related: there is good reason(s) and sufficient evidence to assume that there is a causal relationship with the treatment and the AE. Not related: there is good reason(s) and sufficient evidence to exclude a causal relationship with the treatment.

All AEs will require the investigator to obtain adequate information to determine the outcome of the AE and to assess whether it meets criteria as a serious adverse event (SAE), which requires immediate notification to the funding agency and ethics review board. The investigator will obtain sufficient information to determine the causality of the AE (i.e. treatment or

other cause); and provide their opinion on causal association (i.e., whether they consider the AE related or not related to the study intervention). Subjects will receive follow up until the AE either resolves completely or stabilizes to a level acceptable to the investigator.

All SAEs will be reported within 24 hours of the investigator's knowledge of the event to the ethics review board and/or funding agency. An SAE is any AE during the time period of the study that: 1) results in death, 2) is life threatening and places the subject at immediate risk of death, 3) results in in-patient hospitalization, 4) results in significant disability/incapacity, where the disability is a substantial disruption of a person's ability to conduct normal daily life functions, 5) is an important medical event that may not result in death, be life threatening, or require inpatient hospitalization, but which based upon the appropriate medical judgment may require medical and/or surgical intervention to prevent one of the outcomes listed above.

- 7) All data will be reviewed by Drs. [name] and [name] for completeness and accuracy
- 8) Should a temporary or permanent suspension of the study occur, in addition to the PPHS, we would need to inform the funding agency and the NIH.

j) Withdrawal of Subjects

Participants may withdraw from the study at any time, with an early withdrawal, a follow-up visit to examine and ensure patient safety. Withdrawal or discontinuation due to an AE will be distinguished from withdrawal/discontinuation due to an insufficient response to the study treatment. It is rare that the study team will request a subject be withdrawn from the study because the treatment is standard of care, but if an adverse event does occur requiring the subject be withdrawn, a follow up visit to examine and ensure patient safety will be performed.

6) Risks to Subjects

The risks of BoNT injection will be reviewed with patients again at time of enrollment in this protocol. The possible side effects are:

- Over relaxation or muscle weakness of the targeted muscles. Furthermore, non-targeted muscles may be affected.
- Participants may experience pain and discomfort while receiving the injections.
- Infection at the injection site.
- A possibility the muscles will not be targeted similar to your previous treatments and you may not experience the same results as previous clinical treatments.

- Treatment of BoNT to subjects with breathing or swallowing problems poses substantial risks. Muscles in the neck that help in breathing and swallowing may be over relaxed. Subjects may experience severe breathing problems, and inability to swallow. Food and water may also enter the lungs. This potential risk is limited in this study because the muscles being injected are not in the neck but in the arm and hand.
- Allergic reaction, and/or skin or eye irritation
- Nausea
- Skin inflammation (dermatitis)
- The spread of BoNT may be life-threatening and may even lead to death, but this would be a rare occurrence due to the location of the study drug being injected.
- Bad effects have been seen in pregnant animals who were given Botox. Please tell your study doctors immediately if you get pregnant while on this study. If you become pregnant, you will be removed from the study.
- Risk of being videotaped is loss of confidentiality. To reduce this we will not include any personal information, such as your name, with the recording. We will discuss this with you prior to any recording and we will ask you to sign a separate video agreement for this.

There is no difference in procedures and associated risks due to participation in this protocol then treatment for clinical care.

There is some discomfort and local pain associated with insulated EMG injection needles or wire insertions as well as with the current delivered during electrical stimulation. Some patients have discomfort for 1-3 hours after hooked wire insertion, but most tolerate the procedure well. Patients are free to discontinue diagnostic testing or injection at any time.

There is no medical risk with ultrasound. There may be mild discomfort or skin irritation with the coupling gel used on the transducer.

There is a very small risk that the muscles will not be targeted equally due to using only one of the targeting methods to identify the muscle and subject could possibly not have results of previous clinical treatments.

There is a risk should a subject be pregnant or become pregnant during the study. These risks are unknown and could minor or major (death). Women of childbearing potential will have a pregnancy test prior to treatments and reminded to continue to use two forms of contraception. Men should not father a child while on this research study and will be requested to use condoms while participating in this study.

The patients have a potential risk for loss of privacy

There is always the possibility for unknown risks to occur

7) Provisions for Research Related Injury

Medical care will be available to participants in the occurrence of any adverse events. NIH will provide medical coverage for research-related injury in accordance with NIH policy. For those enrolled the Icahn School of Medicine site, the participant and his/her insurance company will be responsible for the medical costs

8) Potential Benefits to Subjects

Indirect benefits:

This study does not offer direct benefit to participants but is likely to yield generalizable knowledge about the best therapy paradigms using ona-BoNT. While there are no direct benefits to the participants, injections of BoNT may alleviate over-active muscles.

9) Provisions to Protect the Privacy Interests of Subjects

All study visits will occur in private exam rooms. Phone calls and any information concerning the participant's involvement of the study will be conducted with sensitivity of maintaining the participant's privacy.

10) Economic Impact on Subjects

Participants will not be responsible for any costs, and the drug for the treatment visit will be provided without cost to the participants.

11) Payment to Subjects

Participants will receive payments for each study visit for travel in the amount of \$75 to be provided by check in approximately 4-6 weeks after each completed visit. If extra visits are required, these visits will receive compensation at \$75/visit.

12) Consent Process

Consent procedures

The study teams will use the standard operating procedure for conducting the consent form process per the institutional guidelines. Prior to any study activities, participants will be provided a copy of the consent form, and undergo a consent process, which includes signing the consent and providing a copy to the subject prior to any screening activities. Once the consent process is completed, the screening process will be completed.

All participants will receive a verbal explanation in terms suited to their comprehension of the purposes, procedures and potential risks of the study and of their rights as research participants. Participants will have the opportunity to carefully review the written consent form and ask questions regarding this study prior to signing and at each study visit.

Consent documents

The consent document contains all required elements as required by regulations and will be provided to the respective institutions for ethical review. .

Children – N/A; Cognitively Impaired Adults - N/A

Non-English Speaking Subjects

For non-English speaking subjects at Mount Sinai – currently all subjects treated by Drs. [name], [name] and [name] are English speaking. Should a participant become eligible that does speak another language other than English, the IRB will be contacted and the appropriate translation of the consent will be requested from the IRB for approval. The subject will then be included and follow standard procedures for non-English speaking according to MSSM's consent SOP (i.e. include translator during each study visit). The NIH will follow standard procedures for their site when managing non-English speaking subjects. The NIH has a short form consent and the English consent form will be used as the script for the short form consent process.

Waiver or Alteration of the Consent Process – N/A

13) Process to Document Consent in Writing

The Icahn School of Medicine site will use the SOP-091 and the consent will be documented in writing using the standard PPHS consent template.

The NIH will use the standard consent process in writing as required to meet NIH guidelines.

14) Vulnerable Populations

Indicate specifically whether you will include or exclude each of the following populations:

Include	Exclude	Vulnerable Population Type
	x	Adults unable to consent
	x	Individuals who are not yet adults (e.g. infants, children, teenagers)
	x	Wards of the State (e.g. foster children)
	x	Pregnant women
	x	Prisoners

15) Multi-Site Human Research (Coordinating Center)

There will not be a coordinating center, but the grant will be managed by Mount Sinai, the data will be coordinated by the NIH site. Drug will be shipped from the funding agency as a donation to both sites for the study.

16) Community-Based Participatory Research

Not/Applicable

17) **Sharing of Results with Subjects**

Any results which are part of the treatment are available to share with the patient and their clinician.

18) **IRB Review History**

N/A

19) **Control of Drugs, Biologics, or Devices**

Note: The IDS has its own forms that must be completed and a review process that must be followed before the IDS representative will sign off on Appendix B for submission to the PPHS.

N/A

References

- ALTER, K. E. 2010. High-frequency ultrasound guidance for neurotoxin injections. *Phys Med Rehabil Clin N Am*, 21, 607-30.
